Study Duration	Screening (up to 60 days); vaccination to final blood draw (70 days); telephone follow-up: 6 months after final dose; immunology analysis (12 weeks); data analysis and report writing (2 months). Advancement between cohorts will be reviewed by the Protocol Safety Review Team (PSRT) and occur upon review of safety data through 7 days after the 3 rd dose (approximately 2-4 weeks between cohorts). The clinical phase of the study will last for approximately 1 year followed by another year of data analysis and report writing.	
Study Objectives	
Primary: Evaluate the safety of detoxified Shigella flexneri 2a Invaplex_{AR} (Invaplex_{AR}-DETOX) administered by intramuscular (IM) immunization.
 
Secondary: Evaluate immune responses (serum IgG/IgA and ALS IgG/IgA) following IM immunization with Invaplex_{AR}-DETOX.
 
Exploratory:
 
 • Collect samples from vaccinated subjects for exploratory immunological assays. • Perform secondary immunology analyses. • Collect samples for evaluation of C-reactive protein (CRP) responses to the vaccine and placebo. 	

Study Design	
This is a randomized, double-blind, placebo-controlled, Phase 1 clinical trial in which a total of 60 subjects will receive one of three doses of Invaplex_{AR}-DETOX or placebo (saline), as shown in the table below. The vaccine will be administered via IM injection on study days 1, 22, and 43. Each subject will receive the same formulation at each vaccination dependent upon group assignment.
 
The study will be initiated with the lowest dose level (2.5 µg) and will proceed to the next highest dose in an escalating fashion. A dose-level with no occurrence of stopping criteria in the 7 days following the third vaccine dose will prompt moving to the next higher level. All safety data will be summarized and reviewed by the PSRT prior to dose-escalation.
 
For the initial cohort, enrollment will be limited initially to 4 subjects receiving 2.5 µg of Invaplex_{AR}-DETOX alone and 1 subject receiving placebo. If no unexpected symptoms occur within 7 days following initial vaccination, enrollment of the remaining subjects in the cohort may proceed.
 
  
 Cohort	Group	n	Route	Invaplex_{AR}-DETOX (µg)	
   
 A	A-1	16	IM	2.5	
 
 A-2	4	IM	Placebo	
 
 B	B-1	16	IM	10	
 
 B-2	4	IM	Placebo	
 
 C	C-1	16	IM	25	
 
 C-2	4	IM	Placebo	
  
 
Specimens will be collected at prescribed intervals to examine systemic and mucosal immune responses. Vaccine safety will be actively monitored during vaccination and for 28 days following the third vaccine dose. Additionally, a telephone follow-up will be performed at 6 months following receipt of the final vaccination to assess for adverse events.
	Cohort	Group	n	Route	Invaplex _{AR} -DETOX (µg)	A	A-1	16	IM	2.5	A-2	4	IM	Placebo	B	B-1	16	IM	10	B-2	4	IM	Placebo	C	C-1	16	IM	25	C-2	4	IM	Placebo
Cohort	Group	n	Route	Invaplex _{AR} -DETOX (µg)																													
A	A-1	16	IM	2.5																													
	A-2	4	IM	Placebo																													
B	B-1	16	IM	10																													
	B-2	4	IM	Placebo																													
C	C-1	16	IM	25																													
	C-2	4	IM	Placebo																													
Primary Clinical Outcome	
The primary clinical outcome for this study is the assessment of safety and tolerability of Invaplex_{AR}-DETOX. All subjects receiving investigational product will be included in the safety assessment. For safety laboratory data, including hematology, serology, and chemistry parameters, blood will be collected at screening and study days as per the Time and Events Schedule (Table 8). Post-vaccination safety monitoring will include laboratory and clinical evaluations following each vaccine/placebo administration, including assessment of post-vaccination local and systemic reactions through targeted physical exams, symptom surveys, symptom diaries, and other adverse event (AE) monitoring.
																																
Immunology Outcomes	
Primary Immunology Outcomes: The primary immunological outcomes will be Antibodies in Lymphocyte Supernatant (ALS) and antibody (IgG and IgA) titers against Invaplex using methods previously established. Seroconversion will be defined as a ≥ 4-fold increase in endpoint titer between pre-and post-vaccination samples. Peripheral Blood Mononuclear Cells (PBMCs) will be collected to determine antigen-specific IgG and IgA titers in ALS samples. High-titer specimens will be included on each plate to track day to day inter-assay variation. For each antigen, pre- and post-vaccination serum samples will be assayed side-by-side. The antibody titer assigned to each sample will represent the geometric mean of duplicate tests. Reciprocal endpoint titers less than the starting dilution of the assay will be assigned a value of half the starting dilution for computational purposes.
 
Secondary and Exploratory Evaluations: Serologic and ALS (IgG and IgA) responses to additional antigens (S. flexneri 2a LPS, IpaB, IpaC) may be assessed depending on sample availability. IgM and IgG subclass responses (serum and ALS) to key antigens may also be assessed. Serum bactericidal (SBA) titers against S. flexneri 2a 2457T will be determined for pre- and post-vaccination samples. An SBA responder will be defined as ≥ 9-fold increase in SBA titer as
																																

	compared to baseline SBA titers. Samples will be collected, processed, and archived for analysis. PBMCs will be collected for antigen-specific memory B and T cell analysis, antibody secreting cell assay and $\alpha 4\beta 7+$ B cells. Stool samples will be collected to assess antigen-specific fecal IgA and IgG responses. A fecal response will be defined as a ≥ 4 -fold increase from baseline. Concurrently, saliva samples may be collected to assess mucosal IgA and IgG antibody responses.
Hypotheses	Safety: One or more of the proposed dosing regimens will have an acceptable frequency and severity of adverse events. Immunogenicity: 
 IM administration of Invaplex_{AR}-DETOX will induce serum IgG antibody responses to S. flexneri 2a Invaplex in $\geq 50\%$ of subjects in at least one of the study groups. IM administration of Invaplex_{AR}-DETOX will induce antibody responses to either IpaB or IpaC in $\geq 50\%$ of subjects in at least one of the study groups.
Estimated Number of Subjects Screened	Based on prior studies with similar study designs, sample collections and inclusion/exclusion criteria, we anticipate screening approximately 5 subjects for every one subject that is enrolled in the study. Therefore we anticipate approximately 300 individuals will be screened.
Maximum Number of Subjects Enrolled	A maximum of 60 subjects are planned for this study. Up to four alternates per group will be selected that may be enrolled in the event a subject becomes ineligible prior to receipt of the investigational product. Subjects receiving at least one dose of the vaccine (or placebo) will not be replaced.
Eligibility Criteria	Inclusion Criteria: 
 Healthy, adult, male or female, age 18 to 50 years (inclusive) at the time of enrollment. Completion and review of comprehension test (achieved $\geq 70\%$ accuracy, two attempts allowed). Provide written informed consent before initiation of any study procedures. Agrees to complete all study visits and procedures and to provide a screening stool sample. Women of childbearing capacity: Negative pregnancy test with understanding (through informed consent process) to not become pregnant during the study or within three (3) months following the last vaccine dose. Exclusion Criteria: General health 
 Health problems (for example, chronic medical conditions such as psychiatric conditions, diabetes mellitus, hypertension, or any other conditions that might place the subjects at increased risk of adverse events)- study clinicians, in consultation with the PI, will use clinical judgment on a case-by-case basis to assess safety risks under this criterion. The PI will consult with the Research Monitor as appropriate. History of autoimmune disorders, cardiovascular and renal disease. Use of immunosuppressive medications (systemic corticosteroids or chemotherapeutics that may influence antibody development), or immunosuppressive illness, including IgA deficiency (defined by serum IgA <7mg/dL). Women who are pregnant or planning to become pregnant during the study period plus 3 months beyond the last vaccine dose and currently nursing women.

	
 Participation in research involving another investigational product (defined as receipt of an investigational product or exposure to an invasive investigational device) 30 days before planned date of first vaccination or anytime throughout the duration of the study until the last in-clinic study safety visit. Positive blood test for HBsAG, HCV Ab, HIV-1/HIV-2 Ab. Clinically significant abnormalities on basic laboratory screening tests. Systemic antimicrobial treatment (i.e., topical treatments are not an exclusion) within 1 week before administration of the first vaccine dose. 
Research specific
 
 Allergies that may increase the risk of AEs. Regular use (weekly or more often) of antidiarrheal, anti-constipation, or antacid therapy. Abnormal stool pattern (fewer than 3 stools per week or more than 3 stools per day) on a regular basis; loose or liquid stools on other than an occasional basis. Personal or family history of an inflammatory arthritis. Positive blood test for HLA-B27 (associated with increased risk of reactive arthritis secondary to Shigella infection) History of allergy to any vaccine. Exclusionary skin disease history/findings that would confound assessment or prevent appropriate local monitoring of AEs, or possibly increase the risk of a local AE. 
Prior Exposure to Shigella
 
 Serum IgG titer > 2500 to Shigella flexneri 2a LPS. History of microbiologically confirmed Shigella infection. Received previous licensed or experimental Shigella vaccine or live Shigella challenge. Travel to countries where Shigella or other enteric infections are endemic (most of the developing world) within two years prior to dosing (clinician judgement). Occupation involving handling of Shigella bacteria currently, or in the past 3 years.
Sample Size	
The sample size of this study is limited by the early stage (Phase 1) of the product concept/testing and is designed to evaluate preliminary safety data but not designed to show statistically significant differences between groups. Given the small number of subjects per group, the precision of our estimate for adverse events is limited. For example, using binomial probability formula for no observed adverse events within the 16 subjects per group yields a 95% confidence interval of 0-21%. Follow-on studies evaluating seemingly safe and immunogenic doses will be required with larger numbers of volunteers in order to better define the safety profile.

Statistical Methods	
Rates of all adverse events will be analyzed by Pearson's Chi-square test (or Fisher's exact test if assumptions are not met for Pearson's Chi-square), to compare groups, if applicable. Summary tables will be created to indicate the number of subjects who experience events. Vaccine-related events (definitely, probably, or possibly related) will be tabulated by study group. In addition, tables will be prepared to list each adverse event, the number of subjects in each treatment group who experienced an event at least once, and the rate of subjects with adverse event(s). Adverse events will be divided into defined severity grades (mild, moderate, severe, potentially life-threatening). The tables will also

	
divide the adverse events by relationship to the investigational product if applicable. All immunized subjects will be included in the safety analysis.
 
For immunology responses, both qualitative (responder rates) and quantitative (e.g., \log_{10} transformed values) results will be analyzed. Geometric mean titers will be calculated for serologic and ALS responses along with their 95% confidence intervals (or standard deviation). If appropriate, between groups comparisons will be examined with nonparametric median tests (Kruskal-Wallis for continuous data and Fisher's exact tests for categorical data) unless assumptions are fulfilled for Student's t or χ^2.
 
Additional comparisons may be made using repeated measures analysis of variance with study group as the between subject factor and sample collection time-points as the repeated factor. All statistical tests will be interpreted in a two-tailed fashion using an alpha = 0.05 to represent statistical significance.

--	--

3. Table of Contents, List of Tables and List of Figures

Table of Contents

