Shigellosis or bacillary dysentery is a food- and waterborne disease predominantly implicated in children < 5 years of age. Estimates of *Shigella*-associated morbidity and mortality range from 0.1 to 1.1 million deaths (60% in children under 5) and from 90 to 165 million cases of dysentery annually [2, 3]. In military populations, *Shigella* species are a common cause of travelers' diarrhea (TD) responsible for approximately 7% of TD cases [4]. In addition to the acute morbidity of diarrhea in this population, shigellosis is linked to several post-infectious sequelae including irritable bowel syndrome (IBS) and reactive arthritis [5-7].

As *Shigella* species invade the intestinal mucosa, the disease is less amenable to the salutary effects of oral rehydration compared to enterotoxigenic pathogens that cause dehydrating diarrhea [8]. Therefore, antibiotics are frequently required for treatment; however, increasing resistance to fluoroquinolones and cephalosporins (extended spectrum β -lactamases) is undermining efficacy. As therapeutic options narrow, the need for a safe and effective *Shigella* vaccine becomes more pressing. An expert panel convened by the Child Health and Nutrition Research Initiative (CHNRI) of the World Bank identified *Shigella* as one of the highest priorities for long-term vaccine development [2]. Furthermore, the Department of Defense (DoD) has issued directives for the development of vaccines against Campylobacter, enterotoxigenic *Escherichia coli* (ETEC), and *Shigella* (DoD Directive 6205.3; BUMEDINSTR 5450.171).

There are 4 different species [and 47 antigenically distinct serotypes of *Shigella*, divided on the basis of differences in their outer membrane lipopolysaccharide antigen (LPS)], which are *Shigella dysenteriae* (13 serotypes), *S. flexneri* (16 serotypes), *S. boydii* (18 serotypes), and *S. sonnei* (1 serotype) [2]. The multiple and evolving serotypes require the development of polyvalent vaccines [9]. Recent vaccine development efforts have targeted *S. flexneri* 2a, 3a, and 6 as well as *S. sonnei* in an effort to provide broad coverage against the most predominant *Shigella* strains.

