8.8. Duration of Subject Participation

Screening of volunteers will occur during a period of up to 60 days prior to initial vaccinations. Subjects will receive 3 vaccinations on Days 1, 22, and 43. Clinical follow-up will occur as delineated in the Time and Events schedule (Table 8). A phone survey will occur at approximately 6 months after the final vaccine dose. This phone survey will specifically inquire if the subject has experienced any new serious health problems or hospitalizations since their last study follow-up. Inclusion criteria require that a subject be available for the required follow-up period and scheduled clinic visits. Therefore, no military subjects will be enrolled in the study if a known deployment is to conflict with his or her involvement. If there is an unexpected deployment, efforts (e.g., telephone, e-mail, command mail) will be undertaken to obtain safety follow-up data per the protocol schedule.

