8.12.1.7. Theoretical Risks

Post-infection reactive arthritis, characterized as an asymmetric, oligoarticular arthritis commonly involves the knees, ankles, or wrists is known to occur following *Shigella* infection. Some data suggests that the risk of reactive arthritis following shigellosis may be higher in persons carrying the Human Leukocyte Antigen (HLA)-B27 antigen [20]. There is enough uncertainty as to the etiology of arthritis, that a specific entry criteria related to this theoretical risk is included and will exclude volunteers with a personal or immediate family history of inflammatory arthritis or HLA-B27 positivity.

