11.5.4.5. HLA-B27 Screen

Serologic evidence of HLA-B27 will be obtained during the screening process (Days -60 to -9). Evidence of HLA-B27 positivity will make a subject ineligible.

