11.6.1. Adverse Event or Suspected Adverse Reaction

An AE, as defined by the ICH guideline for GCP, is “Adverse event means any untoward medical occurrence associated with the use of a drug in humans, whether or not considered drug related.”

Suspected adverse reaction means any AE for which there is a reasonable possibility that the drug caused the AE. For the purposes of IND safety reporting, “reasonable” possibility means there is evidence to suggest a causal relationship between the drug and the adverse event. Suspected adverse reaction implies a lesser degree of certainty about causality than adverse reaction, which means any adverse event caused by a drug.

An AE is considered any adverse change or exacerbation from a baseline condition that occurs following the initial administration of an investigational product whether or not the event is considered to be related to the investigational product. Examples of this include but are not limited to the following:

- Adverse changes including new signs and symptoms, intercurrent illness modifying the clinical course, or the worsening of a baseline condition including the increased frequency of an event or an increased intensity of a condition
- Concomitant disease with onset or increased severity after the start of study product administration
- A new pattern in a preexisting condition occurring after the receipt of investigational product that may signal a clinically meaningful change
- Clinically significant changes in laboratory values

11.6.2. **Solicited Adverse Events**

A solicited AE is a predetermined event, identified in the Investigator's Brochure, which may reflect safety concerns related to the investigational product. The solicited AEs for this study include:

- Site pain
- Site tenderness
- Swelling
- Induration (determined by investigator exam)
- Site redness
- Pruritus
- Fever
- Nausea
- Vomiting
- Abdominal pain
- Diarrhea (loose stools)
- Appetite change
- Fatigue
- Headache
- Myalgias (general pain or soreness in muscles)
- Arthralgias (general pain in joints)
- Malaise

11.6.3. **Serious Adverse Event or Serious Suspected Adverse Reaction**

An AE or suspected adverse reaction is considered "serious" if, in the view of either the investigator or the sponsor it results in any of the following outcomes:

- Death
- Life-threatening AE
- Inpatient hospitalization or prolongation of existing hospitalization

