n												
Mean												
SD												
Median												
Range												
Visit 02 (1 Day post-Dose 1)												
n												
Mean												
SD												
Median												
Range												
Change from Baseline												
n												
Mean												
SD												
Median												
Range												
Continue for all other Visits (days 2, 8, 22, 23, 29, 43, 44, 50, 57, 71)												

A.3.4 Physical Exam

Table 34: Summary of Abnormal Physical Exam Findings Prior to Dose 1 – Safety Population

[figure not shown]
Body System	Visit	InvaplexAR 2.5 µg (N=X)	InvaplexAR 10 µg (N=X)	InvaplexAR 25 µg (N=X)	Placebo (N=X)
Any Abnormality	Screening				
	Day -7				
Skin	Screening				
	Day -7				
HEENT	Screening				
	Day -7				
Lymph Nodes	Screening				
	Day -7				
Respiratory	Screening				
	Day -7				
Cardiovascular	Screening				
	Day -7				
Abdomen	Screening				
	Day -7				
Neurological	Screening				
	Day -7				
Motor	Screening				
	Day -7				
Sensory	Screening				
	Day -7				
Musculoskeletal (Overall)	Screening				
	Day -7				
Musculoskeletal (Joint survey)	Screening				
	Day -7				
Other	Screening				
	Day -7				

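### The Day 223 call, the only contact after Day 71, has no joint question, and the documents disagree on whether it collects non-serious events such as arthritis, the one named theoretical risk

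*Protocol*

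**What the plan says.** **Before vaccination.** Protocol 8.12.1.7 has one entry: "Post-infection reactive arthritis, characterized as an asymmetric, oligoarticular arthritis commonly involves the knees, ankles, or wrists is known to occur following" *Shigella* infection. It states that "a specific entry criteria related to this theoretical risk is included". The Introduction lists "several post-infectious sequelae including irritable bowel syndrome (IBS) and reactive arthritis" among the consequences of shigellosis. Two exclusions follow. One is inflammatory arthritis in the volunteer or the family. The other is HLA-B27, worded in the synopsis as "Positive blood test for HLA-B27 (associated with increased risk of reactive arthritis secondary to" *Shigella* infection, and in 11.5.4.5 as "Evidence of HLA-B27 positivity will make a subject ineligible". SAP Table 34 reports a row labelled "Musculoskeletal (Joint survey") at Screening and Day -7.

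**Dose 1 to Day 71.** The solicited list in Protocol 11.6.2 includes "Arthralgias (general pain in joints"). The diary runs for 7 days after each dose. Protocol 11.5.1 and 11.8.1 also have the solicited symptoms assessed at every visit, and 11.5.3 adds a focused examination each time. General adverse event collection closes 28 days past dose 3, which is Day 71.

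**After Day 71.** The only contact is the Day 223 telephone call. Protocol 8.8 gives its content: "This phone survey will specifically inquire if the subject has experienced any new serious health problems or hospitalizations since their last study follow-up". Sections 8.5.1 and 11.8.1 are equally limited to serious diagnoses, hospital stays or SAEs. SAP 3.1.1 describes the six-month window the same way, and SAP 4.5.1.2 ends non-serious events about 28 days after an injection. Against this, the Study Design row of the synopsis says the call is for adverse events, with no seriousness limit. SAP Table 18 has a block from Visit 11 to Visit 12 with rows for any AE, Grade 2 or greater AE and related AE, each with exact confidence intervals and a p-value.

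**The concern.** The plan takes reactive arthritis seriously enough to exclude volunteers for it and to examine joints before dosing, but follow-up after Day 71 is not matched to that. A subject who develops a swollen knee three months after dose 3 and is treated as an outpatient could truthfully answer no to a question about serious problems and hospital stays.

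Safety is the primary objective, and Table 18 is the in-text summary of it. If the call follows the protocol body, the late rows for non-serious events will be filled from whatever subjects happen to volunteer, then printed with intervals and a test. A row of zeros would look like an observed absence of events when the question was not put.

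**Working it through.** **1. The plan's own precision figure.** Protocol 12.2 and SAP 5 give 0–21% for no events in 16 subjects. The exact two-sided upper limit for 0/n is 1 − 0.025^(1/n). For n = 16 this is 20.6%, which reproduces the stated 21%. For all 48 vaccinees (3 × 16) it is 7.4%. The 7.4% bound applies to non-serious arthritis only over the period in which such events are ascertained, which is to Day 71 under the protocol body.

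**2. Length of the late period.** Days are from Protocol Table 8: dose 3 on Day 43, last clinic visit on Day 71, call on Day 223 ± 28.
- Dose 3 to last visit: 71 − 43 = 28 days.
- Dose 3 to call: 223 − 43 = 180 days.
- Covered only by the call: 223 − 71 = 152 days, or 124 to 180 days across the call window (195 − 71 and 251 − 71).
- Share of the time after dose 3: 152/180 = 84%. Share of all follow-up from Day 1: 152/222 = 68%.

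**3. What the late period is meant to collect.**
- Serious events only: Protocol 8.5.1, 8.8 and 11.8.1; SAP 3.1.1 and 4.5.1.2.
- Any adverse event: Protocol synopsis (Study Design); SAP Table 18, block after Visit 11.
- SAP 8.3 describes Table 18 as covering events within 28 days of the third vaccination, so the SAP text and its own table shell also differ.
- A joint or arthritis question: in none of these places.

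Both sets of statements cannot describe the same call.

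**4. Where a late arthritis would appear.** Tables 19 to 28 give preferred terms but stop at Day 71. After that, Table 18 has only aggregate rows. The event would be named in Listing 10, and in Table 29 or 30 if it met their criteria, provided that it reached the adverse event form.

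**5. Can missed cases be counted?** Not from the documents, which give neither an onset distribution nor a rate after vaccination. The following is an illustration under assumption only, with onset uniform from day 7 to day L after a dose and collection ending at Day 71.
- Dose 3 alone, captured share (28 − 7)/(L − 7): 100% at L = 28, 43% at L = 56, 27% at L = 84.
- Onsets split equally over three doses, with 70, 49 and 28 days of collection: 100% at L = 28; (100 + 86 + 43)/3 = 76% at L = 56; (82 + 55 + 27)/3 = 55% at L = 84.

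The answer runs from no loss to a loss of most dose 3 cases, depending on inputs the documents do not supply.

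**The case against.** The opposing case has real force on several points.

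- A reader might infer that late non-serious arthritis would certainly go unrecorded. The documents do not support that. The synopsis and Table 18 provide for any AE, a subject may volunteer the event, and disabling arthritis can be serious through incapacity or as an important medical event (Protocol 11.6.3). Hospital care is one trigger in the call, not a condition.
- A reader might infer that joint symptoms are asked about only in the 7-day diary windows. Protocol 11.5.1 and 11.8.1 have them surveyed at every clinic visit to Day 71, and Tables 21 to 28 give any reported arthritis its own preferred-term row up to then. Table 34 is a baseline table by its title, so the lack of a later joint survey in it is not a defect.
- Arthritis is not the only risk screened for. Allergy, skin disease and autoimmune history are also exclusions. It is the only one named under Theoretical Risks.
- The protocol describes arthritis after infection, and this product is a purified subunit complex.

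The last point does not remove the gap. Section 8.12.1.7 itself cites uncertainty about the cause as the reason for the entry criterion, and the same uncertainty supports asking afterwards. The synopsis and Table 18 do not settle the matter either, because five other places say the opposite. Spontaneous mention in reply to a question about serious problems is not ascertainment.

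**Conclusion.** The point holds in limited form. Late non-serious arthritis is not specifically solicited, and the documents contradict each other on whether non-serious events are collected at all between Day 71 and Day 223. The period that depends on the single call is 152 of the 180 days after dose 3 (84%), taking scheduled days at face value.

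This length of time should not be read as a proportion of cases lost. The call looks back over the whole interval, and the capture shares in the working rest on an assumed latency. Nor do the documents show that the report would be presented as full six-month safety, since SAP 3.1.1 states the late window as serious problems and Table 18 splits at Visit 11. What they do show is that the late any-AE rows, with their intervals and p-value, would not match what the protocol body has the call ask. This is a cheap improvement to the primary safety objective and a contradiction that needs resolving. It does not invalidate the design.

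**What to change.** 1. In Protocol 8.5.1 and 8.8, add a fixed question to the Day 223 call: any new joint pain or swelling, or a new arthritis diagnosis, since Day 71, with onset date. Record positive answers whatever their seriousness. Add a row for new-onset arthritis, Day 1 to Day 223, by treatment group to SAP Table 18.
2. Reconcile the synopsis (Study Design) and SAP Table 18 with Protocol 8.5.1, 8.8 and 11.8.1 and SAP 3.1.1, 4.5.1.2 and 8.3. Either the call asks for all adverse events and those sections say so, or the late block of Table 18 is cut to the SAE rows plus the new arthritis row. In either case each late row should report only what the call asks about.

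The cost is one question in a call already planned, one eCRF field, one table row and a text alignment, with no extra visit or procedure. The downside is that a few nonspecific joint complaints will be recorded in every arm, with the pooled placebo group as background.
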